4.2. Number of Participants

In Part A, approximately 48 healthy male and female participants (36 randomised to GSK3858279, 12 randomised to placebo) will be enrolled in the study across a maximum of six cohorts (up to five cohorts for IV dosing and one cohort for SC dosing). In each cohort, eight participants will be enrolled, and will be randomised in a 3:1 ratio to GSK3858279: placebo (six will receive GSK3858279 and two will receive placebo). Five evaluable participants are required per cohort, where a participant is considered evaluable if they complete both the screening period and all their planned visits.

In Part B, approximately 50 (a minimum of 20 up to a maximum of 80) participants with OA will be enrolled and will be randomised to receive either GSK3858279 or placebo in a 1:1 ratio A sample-size re-estimation may be performed, and the sample size may be decreased or increased up to a maximum of 80 participants.

For Part A, if participants prematurely discontinue the study, additional participants may be enrolled as replacements (and assigned to the same intervention) at the discretion of the Sponsor in consultation with the investigator.

For Part B, if randomised participants prematurely discontinue the study prior to dosing, additional participants may be enrolled as replacements (and assigned to the same intervention) following Sponsor approval.

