4.3. Scientific Rationale for Study Design

Study population

Part A of this study is the first time GSK3858279 will be given to humans. A healthy population is believed to be appropriate to explore the safety and tolerability of GSK3858279 in a population not currently receiving concomitant therapeutic treatments and whose immune function is not compromised. In the absence of reproductive toxicity data, the study population will be restricted to male participants and females of non-reproductive potential.

Part B of this study will investigate the effects of GSK3858279 on pain. In the absence of human experimental pain models that are CCL17 dependent or accurately predict analgesic effect in OA, and of biomarkers for pain, proof of mechanism is best achieved by assessing clinical endpoints in an OA patient population. Knee OA pain participants will be enrolled because of the high prevalence of the condition and well-established clinical endpoints for pain.

The heightened relative risk of increasing age and BMI to COVID-19 susceptibility and poorer outcomes has been considered [Williamson, 2020]. Inclusion of participants between 40 to 75 years (inclusive) and with a BMI within the range 19-34.9 kg/m² (inclusive) will continue to be permitted in this study because these parameters are inherently associated to and therefore largely cover the OA population. All participants are to be screened and monitored throughout for COVID-19, and mitigation steps have been incorporated.

Control and blinding

As the primary objectives of the study are safety and tolerability of single IV and SC doses (Part A) and repeat SC doses of GSK3858279 (Part B), use of a placebo comparator is required for assessment of the safety profile. A placebo arm will also act as a true negative control for target engagement and pain assessments.

To ensure unbiased outcomes, a double-blind approach is preferable.

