14.11.10. Pharmacodynamic Tables

14.11.10.1. Part A

No.	Population	IDSL / Example Shell	Title	Programming Notes	Deliverable
Serum Target Engagement					
4.01	Safety	PD_T1	Part A: Summary of Free & Total CCL17 in Serum Concentration- Time Data (pg/mL)	
Please only present the median, min, max, sd (log), geometric mean and 95% CI back-transformed from the \log_e scale.
 
Apply logit transformation for % reduction parameter and present median, min, max, sd (logit), geometric mean and 95% CI, back-transformed from the logit scale.
 
If % reduction ≤ 0, set to 0.1.
 
If % reduction ≥ 100, set to 99.9.
 
These imputations are needed for logit transformation.
 
Use Student's t-distribution for CI.
 
Add the following footnotes:
 
Note: Free CCL17 values below the LLOQ have been imputed to $\frac{1}{2}^*$ LLOQ. Total CCL17 values below the LLOQ have been imputed to 0. Values equal to zero at baseline have been imputed to LLOQ whilst missing baseline values have been imputed to the median of the non-missing baseline values.
 
Note: Free CCL17 and Total CCL17 exceeding the upper limit of quantification (ULOQ) have been excluded from the summary statistics (ULOQ Free CCL17: 3600 pg/mL, ULOQ Total CCL17: 50000 pg/mL).
 
Note: If more than 30% of values have been imputed at any timepoint for a treatment group, then the standard deviation is not displayed.
 
Note: Percentage reduction values ≤ 0 are imputed to be 0.1 and values ≥ 100 are imputed to be 99.9.
 
Note: The percentage reduction parameter was logit transformed, summarised, and back-transformed using the logistic function to obtain the geometric summary statistics. The 95% CI of the geometric mean was calculated using Student's t distribution.
	Part A SAC

No.	Population	IDSL / Example Shell	Title	Programming Notes	Deliverable

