4.02	Safety	PD_T2	Part A: Summary of Derived Free and Total CCL17 in Serum Target Engagement Parameters (non- transformed and log- transformed)	
Please only present the median, min, max, sd (log), geometric mean and 95% CI back-transformed from the \log_e scale.
 
Please note that tmax and tmin should not be \log_e-transformed and 95% CI should not be presented.
 
Apply logit transformation for maximum % reduction parameter and present median, min, max, sd (logit), geometric mean and 95% CI back-transformed from the logit scale.
 
If maximum % reduction ≤ 0, set to 0.1.
 
If maximum % reduction ≥ 100, set to 99.9.
 
These imputations are needed for logit transformation.
 
Use Student's t-distribution for CI.
 
Add the following footnote:
 
Note: Percentage reduction values ≤ 0 are imputed to be 0.1 and values ≥ 100 are imputed to be 99.9.
 
Note: The maximum percentage reduction parameter was logit transformed, summarised, and back-transformed using the logistic function to obtain the geometric summary statistics. The 95% CI of the geometric mean was calculated using Student's t distribution.
	Part A SAC

No.	Population	IDS / Example Shell	Title	Programming Notes	Deliverable
Blister Target Engagement					

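### Free CCL17 percent reductions at or below zero are reset to 0.1% so that a logit can be taken, so the group mean and CI depend on that constant and the placebo mean cannot show zero or a rise

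*SAP*

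**What the plan says.** SAP Section 14.11.10.1, Table 4.01 (serum free and total CCL17, Part A) instructs the programmer: "Apply logit transformation for % reduction parameter and present median, min, max, sd (logit), geometric mean and 95% CI, back-transformed from the logit scale". The footnote sets the limits: "Percentage reduction values ≤ 0 are imputed to be 0.1 and values ≥ 100 are imputed to be 99.9". The only reason given is "These imputations are needed for logit transformation". For the interval, "The 95% CI of the geometric mean was calculated using Student's t distribution".

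Table 4.02 extends the rule to the peak effect: "If maximum % reduction ≤ 0, set to 0.1". It also appears in the notes to Tables 4.03 and 4.04 and Figures 4.01 and 4.02 in Part A, and to Tables 4.06 and 4.07 and Figures 4.04 and 4.05 in Part B. Figures 4.01 and 4.04 are individual plots, so there it affects displayed values and not a mean.

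One safeguard is stated for Table 4.01: "If more than 30% of values have been imputed at any timepoint for a treatment group, then the standard deviation is not displayed". It suppresses the SD only, never the mean or the CI, and it does not say whether these replacements count as imputed values.

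Protocol Section 4.2 fixes the Part A cohort size: "six will receive GSK3858279 and two will receive placebo". Protocol Section 4.3 gives placebo a specific role: "A placebo arm will also act as a true negative control for target engagement and pain assessments".

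**The concern.** A percent reduction from baseline runs from large negative values (a rise) up to 100%. The SAP treats it as a proportion between 0 and 100%. The logit is undefined at or below zero, so the data are altered to suit the transformation. Participants exactly at baseline, 5% above it and at double baseline all become the same 0.1%.

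Such values should be expected. Protocol Section 4.4.1 predicts a return to baseline at about three weeks even at 10 mg/kg IV, and Protocol Table 1 has Part A follow-up running 84 to 140 days. On placebo with no true change, about half of the values should be at or above baseline.

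At stake is the reported depth and duration of target engagement, a secondary objective in both parts, and how the placebo comparison reads.

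**Working it through.** The documents give no group mean or CI for percent reduction, so there is no plan figure to reproduce. The check applies the SAP rule to stated examples.

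**Formulas.** SAP method: replace v ≤ 0 by 0.1, take L = ln(v/(100 − v)), average L, form mean ± t × SD/√n, then back-transform with the logistic function. Comparator: r = post-dose/baseline = 1 − v/100, average ln r, report 100 × (1 − exp(mean ln r)), with the CI back-transformed in the same way.

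**Example 1 (hypothetical, n = 6): five at 90%, one 5% above baseline.**
- Logit(90%) = 2.197 and logit(0.1%) = −6.907. Mean = (5 × 2.197 − 6.907)/6 = 0.680, which back-transforms to 66.4%.
- The SD of L is 3.717, so SE = 3.717/√6 = 1.517. With t(5 df) = 2.571 the half-width is 3.90. The limits −3.22 and 4.58 back-transform to 3.8% and 99.0%.
- Ratio method: 1 − (0.1⁵ × 1.05)^(1/6) = 85.2%, CI 59.5% to 94.6%. The median is 90%.
- Changing only the constant: with 1% (logit −4.595) the SAP mean is 74.4%; with 0.01% (logit −9.210) it is 57.3%.
- One replacement in six is 17%, below the 30% threshold, so the SD would be shown too.

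**Example 2: direction of the error (n = 6).** Three at 40% reduction (logit −0.405), three above baseline. The SAP mean logit is (−0.405 − 6.907)/2 = −3.656, or 2.5%, however large the rise.
- If the three are 10% above baseline, the ratio method gives 1 − √(0.6 × 1.1) = 18.8%. The SAP understates.
- If the three are at double baseline, it gives 1 − √(0.6 × 2.0) = −9.5%. The SAP shows a reduction where there is a net rise.

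**Example 3: the protocol's predicted maximum inhibitions (Protocol Table 2), five of six at that value and one at baseline.**

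| Typical value (%) | SAP mean | Plain mean | Ratio method |
|---|---|---|---|
| 99 | 93.6 | 82.5 | 97.8 |
| 98 | 89.0 | 81.7 | 96.2 |
| 96 | 81.7 | 80.0 | 93.2 |
| 86 | 58.9 | 71.7 | 80.6 |
| 56 | 27.9 | 46.7 | 49.5 |

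For the 96% row the SAP CI is 5.6 to 99.7, against 72.8 to 98.3 by ratio.

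**Example 4: placebo.** Six cohorts × 2 = 12, reported under one placebo code. The variability of post-dose/baseline is not in the documents, so a lognormal ratio with CV 10% to 50% is assumed (20,000 simulated groups per setting). The median SAP mean is 0.7% to 1.7% with no true change, 0.1% to 0.7% with a true 20% rise, and 0.1% to 0.3% with a true 50% rise. The result is positive by construction, because the logistic function never reaches zero. The ratio method gives about 0, −20% and −50%.

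**Two side effects.** A value between 0 and 0.1 is left alone, so a true 0.05% reduction ranks below a rise. The upper limit cannot bind for observed free CCL17: values below the LLOQ of 2.93 pg/mL become half of it (1.465), so the reduction stays below 100%.

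**The case against.** The strongest reply is that the remedy is largely on the same page. Table 4.01 also gives the median of percent reduction and log-scale geometric means of concentration. In Example 1 the median is 90%. If the same participants contribute at both times, dividing the post-dose geometric mean by the baseline one recovers the 85%, though not its paired CI. A placebo rise would show there as well, except for values above the ULOQ, which are excluded. This stands, and it limits the consequence. The median helps only while fewer than half of a group is replaced. In Example 2, if it is taken after replacement, it is (40 + 0.1)/2 = 20%, whatever the size of the rise.

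It is also fair to say that the pull is not peculiar to the logit. Above a typical reduction of about 95%, one participant at baseline lowers the SAP mean less than a plain mean. The comparison that counts is with the ratio mean, which needs no replaced values.

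Three stronger readings are tempting, and the documents do not support them.
- A reader might infer that the rule shaped the Part B dose. The repeat SC regimen came in with Amendment 3 (18-JUL-2019), citing an interim report of blinded Part A data dated 11-JUN-2019. The re-analysis came with Amendment 5 (07-SEP-2020). The first SAP is dated 01-MAR-2021, and nothing visible shows the rule in earlier use.
- A reader might infer that engagement is always understated. Example 2 shows the opposite can happen.
- A reader might infer that placebo is useless as a control. A placebo mean near 1% is still distinguishable from predicted peaks of 56% to 99%.

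**Conclusion.** The point holds for the mean and CI of percent reduction in free CCL17. With one of six participants 5% above baseline and the rest at 90%, the SAP mean is about 19 percentage points below the ratio-based value (66.4 against 85.2). It moves between 57% and 74% as the constant goes from 0.01% to 1%, and its CI spans almost the whole scale. A placebo percent-reduction mean cannot read zero or a rise.

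These sizes rest on illustrative groups and, for placebo, on an assumed CV; no observed values are in the documents. These are descriptive secondary summaries, and the visible plan attaches no hypothesis test to them. The harm is to reporting and interpretation, mostly in Part A. In Part B the percent reductions are model-derived (SAP Section 10.1.1.2.2 and Table 4.06), so the effect is probably smaller there unless the stated fallback to observed data is used. It remains worth correcting because the trigger is foreseeable and the SAP's visible text offers no sensitivity analysis.

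**What to change.** For free CCL17 only, compute post-dose/baseline for each participant and summarise it on the log scale. Report 100 × (1 − geometric mean ratio) as percent reduction, with its back-transformed t-based 95% CI. Treat maximum percent reduction in the same way. Remove the 0.1/99.9 replacement from Tables 4.01 to 4.04, 4.06 and 4.07 and from Figures 4.01, 4.02, 4.04 and 4.05, and let individual displays show actual values.

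No new truncation is needed. Free values below LLOQ are already set to half the LLOQ, and zero baselines to LLOQ, so the ratio is positive. Do not carry the change over to total CCL17: its values below LLOQ are set to 0, where a log ratio is undefined.

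The cost is a set of programming-note edits and a re-run of these summaries, with no new data. Some reductions will display as negative, which needs a footnote. Table 4.07 is also an Interim Analysis 3 deliverable, so any version already produced under the old rule should be labelled as such.

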10.1.5. Statistical Analyses / Methods

Details of the planned displays are presented in [Appendix 11](#) and will be based on GSK Data Standards and statistical principles.

Unless otherwise specified, endpoints / variables defined in Section [10.1.1](#) will be summarised using descriptive statistics, graphically presented (where appropriate) and listed.

cci

The within subject and timepoint blister fluid:serum concentration ratio for free and total CCL17 may be determined from the concentration-time data if data permit. The free and total CCL17 concentrations will be summarised using descriptive statistics, graphically presented (where appropriate) and listed.

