4.03.	Blister	PD_T1	Part A: Summary of Free & Total CCL17 in Blister Fluid Concentration- Time Data (pg/mL)	
Please only present the median, min, max, sd (log), geometric mean and 95% CI back-transformed from the \log_e scale.
 
Apply logit transformation for % reduction parameter and present median, min, max, sd (logit), geometric mean and 95% CI back-transformed from the logit scale.
 
If % reduction ≤ 0, set to 0.1.
 
If % reduction ≥ 100, set to 99.9.
 
These imputations are needed for logit transformation.
 
Use Student's t-distribution for CI.
 
Add the following footnotes:
 
Note: Free CCL17 values below the LLOQ have been imputed to $\frac{1}{2}^*LLOQ$. Total CCL17 values below the LLOQ have been imputed to 0. Values equal to zero at baseline have been imputed to LLOQ whilst missing baseline values have been imputed to the median of the non-missing baseline values.
 
Note: Free CCL17 and Total CCL17 exceeding the upper limit of quantification (ULOQ) have been excluded from the summary statistics (ULOQ Free CCL17: 3600 pg/mL, ULOQ Total CCL17: 50000 pg/mL).
 
Note: If more than 30% of values have been imputed at any timepoint for a treatment group, then the standard deviation is not displayed.
 
Note: Percentage reduction values ≤ 0 are imputed to be 0.1 and values ≥ 100 are imputed to be 99.9.
 
Note: The percentage reduction parameter was logit transformed, summarised, and back-transformed using the logistic function to obtain the geometric summary statistics. The 95% CI of the geometric mean was calculated using Student's t distribution.
	Part A SAC
4.04.	Blister	PD_T1	Part A: Summary of Derived Blister	
Please only present the median, min, max, sd (log), geometric mean and 95% CI back-transformed from the \log_e scale.
 
Apply logit transformation for % reduction parameter and present median, min, max,
	Part A SAC

No.	Population	IDSL / Example Shell	Title	Programming Notes	Deliverable

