			Fluid:Serum Free & Total CCL17 concentration ratio	
sd (logit), geometric mean and 95% CI back-transformed from the logit scale.
 
If % reduction ≤ 0, set to 0.1.
 
If % reduction ≥ 100, set to 99.9.
 
These imputations are needed for logit transformation.
 
Use Student's t-distribution for CI.
 
Please only present the median, min, max, sd (log), geometric mean and 95% CI back-transformed from the loge scale.
 
Apply logit transformation for % reduction parameter and present median, min, max, sd (logit), geometric mean and 95% CI back-transformed from the logit scale.
 
If % reduction ≤ 0, set to 0.1.
 
If % reduction ≥ 100, set to 99.9.
 
These imputations are needed for logit transformation.
 
Use Student's t-distribution for CI.
 
Add the following footnotes:
 
Note: Free CCL17 values below the LLOQ have been imputed to $\frac{1}{2}^*LLOQ$. Total CCL17 values below the LLOQ have been imputed to 0. Values equal to zero at baseline have been imputed to LLOQ whilst missing baseline values have been imputed to the median of the non-missing baseline values.
 
Note: Free CCL17 and Total CCL17 exceeding the upper limit of quantification (ULOQ) have been excluded from the summary statistics (ULOQ Free CCL17: 3600 pg/mL, ULOQ Total CCL17: 50000 pg/mL).
 
Note: If more than 30% of values have been imputed at any timepoint for a treatment group, then the standard deviation is not displayed.
 
Note: Percentage reduction values ≤ 0 are imputed to be 0.1 and values ≥ 100 are imputed to be 99.9.
 
Note: The percentage reduction parameter was logit transformed, summarised, and back-transformed using the logistic function to obtain the geometric summary statistics. The 95% CI of the geometric mean was calculated using Student's t
	

CONFIDENTIAL

207804

No.	Population	IDSL / Example Shell	Title	Programming Notes	Deliverable
				distribution.	
Immunogenicity					
4.05	Safety	IMM1	Part A: Summary of Immunogenicity		Part A SAC

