14.11.11. Pharmacodynamic Figures

14.11.11.1. Part A

No.	Population	IDSL / Example Shell	Title	Programming Notes	Deliverable
Serum Target Engagement					
4.01.	Safety	PK16	Part A: Individual Free & Total Serum CCL17 Concentration-Time Plots (Linear and Semi-log)	
One panel per dose group.
 
Add the following footnotes:
 
Note: Free CCL17 LLOQ = 2.93 pg/mL, ULOQ = 3600 pg/mL.
 
Note: Total CCL17 LLOQ = 13.11 pg/mL, ULOQ = 50000 pg/mL.
 
Note: The baseline value is presented at an actual relative time of 0 days.
 
Note: Any non-quantifiable (NQ) Free CCL17 concentration values have been set to $\frac{1}{2}^*\text{LLOQ}$.
 
Note: Any NQ Total CCL17 concentration values before the first measurable concentration have been set to 0 and have been included in the linear plot.
 
Note: Any single NQ values have been omitted.
 
Note: Any multiple mid-profile NQ concentrations of Free CCL17 and Total CCL17 have been set to $\frac{1}{2}^*\text{LLOQ}$ and 0, respectively, and the subsequent measurable concentrations have been retained.
 
Note: Percentage reduction values ≤ 0 are imputed to be 0.1 and values ≥ 100 are imputed to be 99.9
	Part A SAC

No.	Population	IDSL / Example Shell	Title	Programming Notes	Deliverable

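### Table 4.04 forms the blister fluid:serum CCL17 ratio from imputed values, so pairs below the LLOQ give a constant (free) or an unusable ratio (total)

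*SAP*

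**What the plan says.** The text on blister target engagement after SAP 10.1.5 introduces the ratio: "The within subject and timepoint blister fluid:serum concentration ratio for free and total CCL17 may be determined from the concentration-time data if data permit". It gives no visible rule for samples below the LLOQ.

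SAP 14.11.10.1, Table 4.04, is the output ("Fluid:Serum Free & Total CCL17 concentration ratio", Blister population). Its programming note lists the statistics: "Please only present the median, min, max, sd (log), geometric mean and 95% CI back-transformed from the loge scale". Its footnotes match those of Table 4.03, the blister concentration table:

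- "Note: Free CCL17 values below the LLOQ have been imputed to" half the LLOQ.
- Total CCL17 below LLOQ becomes 0. A zero at baseline is then replaced by the LLOQ, and a missing baseline by the median of the non-missing baselines.
- Values above the upper limit are left out of the summary ("ULOQ Free CCL17: 3600 pg/mL, ULOQ Total CCL17: 50000 pg/mL").
- "If more than 30% of values have been imputed at any timepoint for a treatment group, then the standard deviation is not displayed".

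The serum figures in SAP 14.11.11.1 give the assay range: "Note: Free CCL17 LLOQ = 2.93 pg/mL, ULOQ = 3600 pg/mL". No separate blister LLOQ is stated, although Table 4.03 repeats the serum upper limits. Listing 75 prints the individual ratios. Each Part A cohort is small: "six will receive GSK3858279 and two will receive placebo" (Protocol 4.2).

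**The concern.** Half-LLOQ substitution is a common convention for summarising concentrations. It does not carry over to a ratio of two concentrations, because the substituted numbers cancel. The result then describes the assay, not the participant. The zero rule for total CCL17 is worse for this purpose, since a ratio containing a zero has no usable logarithm and the table calls for a geometric mean. The missing-baseline rule would also let a ratio described as within-subject contain a value taken from other participants.

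Target engagement is a secondary objective, and the protocol treats skin as a surrogate for tight tissue. The ratio shows how engagement in that tissue relates to serum. If substituted values accumulate at some doses or timepoints and not others, a difference in the tabulated ratio could reflect the assay floor rather than distribution of the target.

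**Working it through.** The plan states no figure for this ratio, so there is nothing to reproduce. The check is arithmetic on the stated rules.

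**Inputs.** Free CCL17 LLOQ 2.93 pg/mL (SAP 14.11.11.1); six active participants per cohort (Protocol 4.2). Assumptions: true ratio r, and an equal blister LLOQ unless stated.

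**1. Free CCL17, both samples below LLOQ.** Ratio = (0.5 × LLOQ(blister)) / (0.5 × LLOQ(serum)) = LLOQ(blister)/LLOQ(serum). With equal limits this is 1.465/1.465 = 1. If the blister LLOQ were 0.5, 2 or 4 times the serum LLOQ, it would be 0.5, 2 or 4. The true ratio does not enter.

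**2. Free CCL17, one sample below LLOQ.**
- Blister below: the truth is only known to be under LLOQ/serum. The table enters half that bound.
- Serum below: the truth is only known to exceed blister/LLOQ. The table enters twice that bound.

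**3. Total CCL17, post-baseline.** Blister below LLOQ gives 0/serum = 0. Serum below gives blister/0, which is infinite. Both below gives 0/0. None can be log-transformed.

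**4. Effect on the geometric mean.** With m of 6 ratios fixed at 1 and the rest centred on r, the geometric mean is r^((6−m)/6).

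| True r | m = 1 | m = 2 | m = 3 | m = 6 |
|---|---|---|---|---|
| 0.2 | 0.26 | 0.34 | 0.45 | 1.00 |
| 0.5 | 0.56 | 0.63 | 0.71 | 1.00 |
| 5 | 3.82 | 2.92 | 2.24 | 1.00 |

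**5. The 30% rule.** If each such pair counts as one imputed value, 1/6 = 17% leaves the SD on display and 2/6 = 33% removes it. The geometric mean, CI, median, minimum and maximum are printed in both cases.

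**6. Effect on the CI.** Assume the quantifiable log-ratios have SD 0.5. The log-variance is then [(5−m) × 0.25 + (m(6−m)/6) × (ln r)²]/5 for m = 1 to 5.
- r = 0.2, where (ln r)² = 2.59: m = 1 gives (1.00 + 2.16)/5 = 0.632, SD 0.79; m = 3 gives (0.50 + 3.89)/5 = 0.877, SD 0.94; m = 5 gives 2.16/5 = 0.432, SD 0.66. All exceed 0.5, so the CI widens.
- r = 1: m = 3 gives 0.50/5 = 0.10, SD 0.32, so the CI narrows.
- m = 6: SD 0 and a CI of zero width, for any r.

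**7. How often.** A sample falls below 2.93 pg/mL when baseline is below 2.93/(1 − suppression): 5.86 pg/mL at 50%, 73 at 96%, 146.5 at 98% and 293 at 99%. Baseline levels are not given. The 96–99% in Protocol Table 2 is an average over the first 12 hours, whereas post-dose blister fluid is aspirated on Day 8 and again on Day 29 (3 and 10 mg/kg IV, and SC) or Day 43 (1 mg/kg IV). For 10 mg/kg IV, Protocol 4.4.1 predicts half recovery after 9.5 days, so Day 8 suppression lies roughly between 50% and 99%. The corresponding baseline threshold is anywhere from about 6 to 293 pg/mL. The same model returns to baseline at about three weeks, before Day 29; the alternative model in that section predicts longer engagement. The frequency cannot be fixed from these figures.

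**The case against.** The strongest reply is that the governing rule may be out of sight. SAP 10.1.1.1 sends handling of target-engagement concentrations to Section 14.5.4, which is not visible in the public copy, and the table shells are a separate document. The parallel PK section does apply a rule for non-quantifiable values. A similar rule for CCL17 may exist, so it cannot be said that the plan has none. It can be said that the footnote on the ratio table prescribes imputation, and a hidden rule would have to contradict it.

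The footnote also looks pasted: it carries percent-reduction and logit notes that do not fit a ratio. That is probably how it arose, and it is a reason to correct it. The condition that the data must permit the ratio leaves discretion but sets no rule for these pairs. Loss of the SD does signal heavy imputation, without correcting the mean or CI.

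The point about importance stands. The ratio is optional, descriptive and confined to Part A. Blister concentrations are summarised directly in Table 4.03, and no visible decision depends on the ratio.

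Two stronger readings are tempting. A reader might infer from Table 2 that most ratios at effective doses will be driven to 1. That table describes the first 12 hours, no post-dose blister is taken then, and baselines are unknown. A reader might also infer that repeated constants always make the CI too narrow. Step 6 shows that it can widen, and that it collapses only when all pairs are constant.

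**Conclusion.** The point holds as a minor defect in one descriptive table and its listing. Applied as written, the footnote turns free CCL17 pairs with both samples below LLOQ into a constant, enters bounds as observations, and makes affected post-baseline total ratios impossible to summarise on the log scale. For a true ratio of 0.2 in a cohort of six, one to three constant pairs raise the geometric mean from 0.20 to between 0.26 and 0.45. Those figures assume equal LLOQs in the two matrices; with unequal limits the pull is toward another constant. The frequency is unknown, and the CI may move in either direction. The Part B pain endpoints are unaffected.

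**What to change.** In Table 4.04 and Listing 75:

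- Remove the LLOQ and missing-baseline imputation from the ratio, for both free and total CCL17. The percent-reduction notes can go at the same time.
- Show the ratio as not calculable when both samples are below LLOQ, and as a < or > bound when one is.
- Summarise only ratios with both samples quantifiable, and print the number of participants in each category by dose and timepoint.
- State the blister LLOQ.
- Add a footnote saying that the summary covers a selected, less suppressed subset.

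The cost is one programming rule and revised footnotes; if Part A has already been reported, it is a re-run or annotation of one table and one listing. The drawback is a smaller summary at strongly suppressed timepoints and informative selection, since the most suppressed participants drop out. The category counts make that visible but do not remove it.
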